## **6.5 Concomitant Therapy**

Any medication or vaccine (including over-the-counter or prescription medicines, vitamins, and/or herbal supplements or other specific categories of interest) that the participant is receiving at the time of enrollment or receives during the study must be recorded along with:

- Reason for use
- Dates of administration including start and end dates
- Dosage information including dose and frequency

The Study Physician should be contacted if there are any questions regarding concomitant or prior therapy.

The Investigator must be informed as soon as possible about any medication taken from the time of screening until the end of the clinical treatment phase of the study including the 28-day follow-up period following the last dose of study intervention.

Best supportive care should be entered as a concomitant medication in the eCRF.

### **6.5.1 Premedications**

All participants must be receiving treatment with a PPI at the start of the study. Treatment with a PPI can begin at any time prior to enrollment, provided participants have received PPI

treatment for at least 24 hours prior to the first dose of acalabrutinib suspension. Any PPI is permitted, provided it meets the minimum equivalent daily dose of 20 mg rabeprazole.

Participants in the ICU may receive higher doses of PPI, and medications more appropriate for NG tube delivery, such as esomeprazole or lansoprazole. Higher doses of PPIs are allowed, if medically necessary. Please refer to Appendix H for equivalency charts.

If a participant no longer requires PPIs during the course of treatment, PPIs may be stopped. Please refer to treatment guidelines (Section 6.1.2) in such cases.

Any other premedication prior to treatment with acalabrutinib suspension is not necessary, but steroids as premedication for hypersensitivity reactions (eg, CT scan premedication) are allowed.

### **6.5.2 Permitted Concomitant Therapy**

Best supportive care for COVID-19 (per Investigator discretion and institutional guidelines) is required for all participants in this study except as listed in Section 5.2 and Section 6.5.3. Given the rapid emergence of new data related to COVID-19, BSC could change during the duration of the study. The use of therapies such as remdesivir, therapeutic plasma, corticosteroids, or other immunomodulatory agents (eg, tocilizumab) is permitted if recommended by local authorities and part of institutional policies or guidelines. The concomitant administration of immunosuppressive agents with acalabrutinib may require additional safety monitoring as determined by the treating clinician. Investigators should maintain prohibitions of certain concurrent medications for other reasons as listed in Section 6.5.3.

### **6.5.3 Prohibited or Restricted Concomitant Therapy**

The medications listed below are prohibited in the study.

#### **Medications Prohibited Through Day 28**

**Immunomodulatory drugs:** Immunomodulatory drugs, intended as treatment for COVID-19 but not considered standard of care according to local institutional guidelines, are prohibited in the study through Day 28. Participants who are taking immunomodulatory drugs for other medical conditions (eg, tocilizumab for rheumatoid arthritis) may continue with treatment upon discussion with the Study Physician.

#### **Medications Prohibited Through Day 14**

**Strong CYP3A inhibitors or inducers:** Drug-drug interactions may occur with some of the drugs being used as BSC (eg, drugs that are strong inducers or strong inhibitors of CYP3A). Concomitant administration with a strong inhibitor of CYP3A has the potential to increase

acalabrutinib exposure. Conversely, concomitant administration with a strong inducer of CYP3A has the potential to decrease exposure of acalabrutinib and could reduce efficacy. Therefore, the concomitant use of strong inhibitors or inducers of CYP3A (see Appendix E) should be avoided in the study. If a participant requires a strong CYP3A inhibitor or inducer while on treatment with acalabrutinib, acalabrutinib treatment must be discontinued. Refer to Section 6.5.4 for additional information on drugs with potential drug-drug interactions.

**Other BTK inhibitors:** BTK inhibitors other than acalabrutinib are prohibited.

**Certain anticoagulants:** Warfarin or equivalent vitamin K antagonists (eg, phenprocoumon) are prohibited in the study. Participants who require prophylaxis or therapeutic anticoagulation for thrombosis (deep vein thrombosis or pulmonary embolism) will be allowed to receive therapeutic anticoagulation with a non-vitamin K inhibitor class of anticoagulants (eg, heparin or low-molecular-weight heparin).

Refer to Section 5.2 for additional restrictions on concomitant therapy.

#### 6.5.4 Acalabrutinib Drug-drug Interaction Guidance in the Presence of Life-threatening COVID-19 Infection

Drug-drug interaction recommendations provided for acalabrutinib in this protocol are made with respect to the presence of life-threatening COVID-19 infection and ability to achieve [REDACTED] occupancy steady-state in target B-cell and monocytic populations. Therefore, the Sponsor recommends that all eligible participants with COVID-19 begin dosing with acalabrutinib 100 mg bid. The duration of acalabrutinib therapy will be limited to 14 days (a maximum of 28 doses). Table 6 provides guidance for participants taking moderate CYP3A inhibitors and acid-reducing agents while on study. Refer to Appendix E for a list of common CYP3A inhibitors/inducers and gastric acid-reducing medicines.

**Table 6 Acalabrutinib Use with Moderate CYP3A Inhibitors and Gastric Acid-reducing Agents**

	Coadministered Medicines	Recommended Acalabrutinib Use
CYP3A Inhibitor	Moderate CYP3A inhibitor	Monitor participants closely for adverse reactions if taking moderate CYP3A inhibitors. For participants who experience an intolerable adverse event (ie, Grade 3-4) attributed to acalabrutinib therapy, reduce the dose to 100 mg once daily.
Gastric Acid Reducing Medicines	H2-receptor antagonists	Take acalabrutinib 2 hours before taking a H2-receptor antagonist.
	Antacids	Separate dosing by $\geq 2$ hours.

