### 2.3.1 Risk Assessment

The safety profile of acalabrutinib in patients with COVID-19 is not yet established. The COVID-19 population is distinct from patients with hematologic malignancies, the population for which acalabrutinib is indicated, and the duration of acalabrutinib treatment for COVID-19 is much shorter than for the indicated population with hematologic malignancies. Therefore, the safety profile of acalabrutinib in the COVID-19 population may differ from that established in the cancer population.

The experience with chronic administration of acalabrutinib in hematologic cancer studies is described below. Table 2 summarizes the risks associated with acalabrutinib (any grade,  $\geq$  Grade 3, and median time to first onset) based on 1040 participants with hematologic malignancies who received acalabrutinib monotherapy (data on file).

Refer to Section 6.6 for acalabrutinib dose modification and toxicity management guidance.

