## **6.6 Dose Modification**

In general, no acalabrutinib dose modification is required if a participant experiences a Grade 1 or Grade 2 AE. Acalabrutinib therapy should be modified or discontinued, however, for the AEs described in Table 7.

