**Table 7 Guidelines for Acalabrutinib Dose Modification or Discontinuation**

Event	Acalabrutinib Dose Modification/Discontinuation
Hematological	
Grade 4 neutrophil count decrease (ANC < 500/ $\mu$ L)	
 
• Hold acalabrutinib, and consider introducing growth factors (eg, G-CSF) and continue to monitor ANC
 
• If neutropenia has improved to Grade 1 or baseline within 3 days of event onset, restart acalabrutinib
 
• If neutropenia has not improved to Grade 1 or baseline within 3 days of event onset, discontinue acalabrutinib
 

Any grade febrile neutropenia lasting more than 2 days	
 
• Discontinue acalabrutinib
 
• Consider introducing growth factors (eg, G-CSF), evaluate participant for infection, and begin antibiotic treatment per institutional guidelines
 

Presence of significant bleeding events with or without thrombocytopenia, such as: 
 
• Grade 3 or 4 hemorrhage
 
• Any grade serious hemorrhage event
 
• Any grade intracranial hemorrhage or hematoma
 
	Discontinue acalabrutinib

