**Table 7 Guidelines for Acalabrutinib Dose Modification or Discontinuation**

Event	Acalabrutinib Dose Modification/Discontinuation
Grade 4 platelet count decrease (< 25,000/mm  )	
 
Hold acalabrutinib and consider platelet transfusions, as clinically indicated
 
If thrombocytopenia has improved to ≤ Grade 2 within 3 days of event onset, restart acalabrutinib
 
If thrombocytopenia has not improved to ≤ Grade 2 within 3 days of event onset, discontinue acalabrutinib
 

Gastrointestinal/hepatic	
Grade 3 or 4 nausea, vomiting, or diarrhea, if persistent despite optimal antiemetic and/or antidiarrheal therapy	Discontinue acalabrutinib
Acute hepatic toxicity or hepatic failure, which is of such severity that after evaluation by a hepatologist, would consider appropriate to stop all non-essential medications	Discontinue acalabrutinib
Cardiovascular	
Grade 3 or 4 hypertension, if persistent despite optimal antihypertensive therapy	Discontinue acalabrutinib
Grade 3 or 4 arrhythmias that are sustained or associated with cardiovascular instability	Discontinue acalabrutinib
Infections	
Severe opportunistic infection (such as Pneumocystis jirovecii pneumonia, toxoplasmosis, disseminated Mycobacterium avium complex, PML)	Discontinue acalabrutinib
Grade 3 confirmed bacterial infections	
 
Hold acalabrutinib
 
If infection does not respond to appropriate antimicrobial therapy within 48 to 72 hours, discontinue acalabrutinib
 

Grade 4 confirmed bacterial infections	Discontinue acalabrutinib
Other	
Any non-COVID-19-related Grade 4 AE	Discontinue acalabrutinib
Any other Grade 3 or Grade 4 toxicity that persists despite optimal medical management	Discontinue acalabrutinib

AE = adverse event; ALT = alanine aminotransferase; ANC = absolute neutrophil count; ALP = alkaline phosphatase; AST = aspartate aminotransferase; G-CSF = granulocyte colony-stimulating factor; PML = progressive multifocal leukoencephalopathy.

Clinical judgment should be used to determine appropriate management of the participant during any AE.

Acalabrutinib may be held for a maximum of 3 consecutive days (6 consecutive doses) from expected dose due to toxicity. If a dose is missed due to an AE or for any other reason, missed

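### For participants on a moderate CYP3A inhibitor, Table 6 lowers the dose for drug-attributed Grade 3-4 events that Table 7 treats by stopping the drug, and no text says which table governs

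*Protocol*

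**What the plan says.** Two sections give dosing instructions for severe toxicity.

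Section 6.5.4 deals with drug interactions. It introduces its table with "Table 6 provides guidance for participants taking moderate CYP3A inhibitors and acid-reducing agents while on study". For moderate CYP3A inhibitors, Table 6 asks for close monitoring and then states: "For participants who experience an intolerable adverse event (ie, Grade 3-4) attributed to acalabrutinib therapy, reduce the dose to 100 mg once daily". It lists no exceptions by type of event.

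Section 6.6 deals with dose modification in general. It states: "Acalabrutinib therapy should be modified or discontinued, however, for the AEs described in Table 7". It makes no exception for users of moderate CYP3A inhibitors. The events for which Table 7 discontinues acalabrutinib include "Grade 3 or 4 hemorrhage", "Grade 4 confirmed bacterial infections", "Any non-COVID-19-related Grade 4 AE", and Grade 3 or 4 arrhythmia that is sustained or accompanied by cardiovascular instability. No row of Table 7 reduces the dose to once daily.

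Three other places bear on the choice between the tables. Section 2.3.1 says: "Refer to Section 6.6 for acalabrutinib dose modification and toxicity management guidance". The text after Table 7 says: "Clinical judgment should be used to determine appropriate management of the participant during any AE". Section 8 sends immediate safety concerns to the sponsor for a decision on whether the participant goes on with treatment.

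**The concern.** A site with a participant on a moderate CYP3A inhibitor who has a severe event attributed to acalabrutinib holds two written instructions that cannot both be followed. Table 6, taken alone, halves the daily dose (from 2 x 100 mg = 200 mg to 100 mg) and keeps treating. Table 7 stops. Hemorrhage matters most, because Section 2.3.1.1 records bleeding events, some of them fatal, in participants treated with acalabrutinib.

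The situation is allowed to arise. Exclusion Criterion 16 and Section 6.5.3 exclude or prohibit only strong CYP3A inhibitors. Appendix E lists ciprofloxacin, erythromycin, fluconazole and verapamil among the moderate ones. Section 6.5.3 also permits therapeutic anticoagulation with agents other than vitamin K antagonists.

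What is at stake is the safety of an individual participant and consistent conduct across sites. The trial is single-arm with no formal testing, so its conclusions do not depend on this.

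**Working it through.** No arithmetic decides this point. The check compares the two tables for one case, a participant on a moderate CYP3A inhibitor with an event attributed to acalabrutinib, and then looks for text that ranks them.

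**Step 1. Compare the actions.**

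| Event attributed to acalabrutinib | Table 6 | Table 7 | Compatible? |
|---|---|---|---|
| Grade 3 or 4 hemorrhage | Reduce to once daily | Discontinue | No |
| Grade 4 confirmed bacterial infection | Reduce | Discontinue | No |
| Grade 4 event unrelated to COVID-19 | Reduce | Discontinue | No |
| Grade 3 or 4 arrhythmia, sustained or unstable | Reduce | Discontinue | No |
| Grade 4 neutrophil or platelet decrease; Grade 3 confirmed bacterial infection | Reduce | Hold first; discontinue if recovery or response is not timely | Yes, if the hold comes first and restart is at once daily |
| Grade 3-4 gastrointestinal event or hypertension persisting despite optimal therapy; other Grade 3-4 toxicity persisting despite optimal management | Reduce | Discontinue | Can be sequential: reduce, then stop if it persists |
| Unlisted Grade 3 event that resolves | Reduce | No instruction | Yes |

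Two notes on the table. First, the row for Grade 4 events unrelated to COVID-19 stands under the heading Other. It has to be read as covering what is not listed above it, since otherwise it would clash with Table 7's own hold rules for Grade 4 cytopenias. The conflict with Table 6 survives that reading. Second, the first four rows are a minimum. Table 7 also discontinues for severe opportunistic infection, febrile neutropenia lasting more than 2 days, and acute hepatic toxicity. Table 7 does not define these by a Grade 3-4 threshold, but particular cases can be Grade 3 or 4 and would then meet the same clash.

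**Step 2. Look for an order of precedence.**

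- Section 6.6: the contrast that introduces Table 7 is with Grade 1 and 2 events, not with Table 6.
- Section 2.3.1: the pointer names Section 6.6 for toxicity management but does not mention Table 6.
- Section 6.5.4: calling Table 6 guidance does not rank it lower, because Table 7 is itself titled as guidelines.
- Section 6.6.1.2: for hepatic impairment the protocol does direct sites to Table 7. Section 6.5.4 has no matching direction for moderate CYP3A inhibitors.
- The clinical-judgment sentence and the sponsor discussion in Section 8 give a way to decide a case, but no rule.

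**Result.** Two stated rules require incompatible actions for at least four kinds of event, and no text ranks them.

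**The case against.** The strongest case on the other side is that the tables do different jobs and a careful reader would not be misled. Table 6 is about a co-medication and is generic on the event. Table 7 is the dose-modification table and names the event. Section 2.3.1 sends readers to Section 6.6, and once Table 7 says stop there is no dose left to reduce. Table 6 keeps a purpose, for Grade 3 events that resolve and for the dose on restart after a hold. There are safeguards too: immediate discussion with the sponsor (Section 8), serious adverse event reports within 24 hours (Section 8.3.9), expedited reporting of ventricular arrhythmias (Section 8.3.12), and Safety Review Committee review of any death or Grade 4 hemorrhage due to acalabrutinib (Section 9.6).

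Most of this stands, and it is why the point is minor. It does not remove the conflict. Table 6 names Grade 4 explicitly and is the rule written for this subgroup, so a site could reasonably take it as an exception to the general table. The event-triggered committee review does not list Grade 3 hemorrhage. Section 8 allows no waivers, so following one table departs from the other.

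Two stronger readings are tempting. A reader might infer that the protocol intends dosing to continue after a severe drug-related bleed. That follows only if Table 6 is read without Section 6.6, and the structure of the protocol points the other way. A reader might also try to size the problem from Table 2, which gives hemorrhage of Grade 3 or higher in 28 of 1040 participants (2.7%). That figure comes from chronic dosing in hematologic malignancy and is not limited to events attributed to the drug. Table 2 puts median onset of major hemorrhage at 9.8 months, against a course of at most 28 doses here. Section 2.3.1 itself warns that the COVID-19 profile may differ, and the protocol gives no rate of moderate CYP3A inhibitor use. No usable expected count follows.

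**Conclusion.** The inconsistency is real and minor. For participants on a moderate CYP3A inhibitor, Table 6 and Table 7 prescribe incompatible actions for at least Grade 3 or 4 hemorrhage, Grade 4 confirmed bacterial infection, any Grade 4 event unrelated to COVID-19, and sustained or unstable Grade 3 or 4 arrhythmia. Table 7 is probably intended to govern, but the protocol leaves that to inference.

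The consequence is confined to participant safety, and the effect on the descriptive analysis is negligible. With about 20 participants and the need for both a moderate CYP3A inhibitor and a severe attributed event of the right kind, few if any would be affected. That is a judgment, since the documents do not supply the rates to calculate it. The conclusion assumes that an event attributed to acalabrutinib is ordinarily not also classed as COVID-19-related. This matters only for the general Grade 4 row; the other three conflicts do not depend on it.

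**What to change.** Add one sentence to the moderate CYP3A inhibitor row of Table 6:

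*This dose reduction applies only when Table 7 does not require discontinuing acalabrutinib; where Table 7 requires a hold, hold first and apply the reduced dose on restart.*

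This keeps the purpose of both tables and settles the restart dose after a hold, which Table 7 does not specify. The cost is one sentence at the next amendment. No change to the sample size, endpoints, assessments or analysis is needed.

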### **Gastric Acid-reducing Medications**

Acalabrutinib solubility decreases with increasing pH. Coadministration of acalabrutinib with an antacid (1 g calcium carbonate) decreased acalabrutinib AUC by 53% in healthy participants.

If the participant has discontinued treatment with a PPI, but treatment with an acid-reducing agent is required, consider using an antacid (eg, calcium carbonate), or an H2-receptor antagonist (eg, famotidine). For use with antacids, separate dosing by at least 2 hours. For H2-receptor antagonists, take acalabrutinib 2 hours before taking the H2-receptor antagonist.

Dose modification of acalabrutinib is not necessary when coadministered with antacids or an H2-receptor antagonist.

Recommendations regarding coadministration with H2-receptor antagonists and antacids are provided in the prescribing information (CALQUENCE 2019).

## **6.6 Dose Modification**

In general, no acalabrutinib dose modification is required if a participant experiences a Grade 1 or Grade 2 AE. Acalabrutinib therapy should be modified or discontinued, however, for the AEs described in Table 7.

**Table 7 Guidelines for Acalabrutinib Dose Modification or Discontinuation**

Event	Acalabrutinib Dose Modification/Discontinuation
Hematological	
Grade 4 neutrophil count decrease (ANC < 500/ $\mu$ L)	
 
• Hold acalabrutinib, and consider introducing growth factors (eg, G-CSF) and continue to monitor ANC
 
• If neutropenia has improved to Grade 1 or baseline within 3 days of event onset, restart acalabrutinib
 
• If neutropenia has not improved to Grade 1 or baseline within 3 days of event onset, discontinue acalabrutinib
 

Any grade febrile neutropenia lasting more than 2 days	
 
• Discontinue acalabrutinib
 
• Consider introducing growth factors (eg, G-CSF), evaluate participant for infection, and begin antibiotic treatment per institutional guidelines
 

Presence of significant bleeding events with or without thrombocytopenia, such as: 
 
• Grade 3 or 4 hemorrhage
 
• Any grade serious hemorrhage event
 
• Any grade intracranial hemorrhage or hematoma
 
	Discontinue acalabrutinib

**Table 7 Guidelines for Acalabrutinib Dose Modification or Discontinuation**

Event	Acalabrutinib Dose Modification/Discontinuation
Grade 4 platelet count decrease (< 25,000/mm  )	
 
Hold acalabrutinib and consider platelet transfusions, as clinically indicated
 
If thrombocytopenia has improved to ≤ Grade 2 within 3 days of event onset, restart acalabrutinib
 
If thrombocytopenia has not improved to ≤ Grade 2 within 3 days of event onset, discontinue acalabrutinib
 

Gastrointestinal/hepatic	
Grade 3 or 4 nausea, vomiting, or diarrhea, if persistent despite optimal antiemetic and/or antidiarrheal therapy	Discontinue acalabrutinib
Acute hepatic toxicity or hepatic failure, which is of such severity that after evaluation by a hepatologist, would consider appropriate to stop all non-essential medications	Discontinue acalabrutinib
Cardiovascular	
Grade 3 or 4 hypertension, if persistent despite optimal antihypertensive therapy	Discontinue acalabrutinib
Grade 3 or 4 arrhythmias that are sustained or associated with cardiovascular instability	Discontinue acalabrutinib
Infections	
Severe opportunistic infection (such as Pneumocystis jirovecii pneumonia, toxoplasmosis, disseminated Mycobacterium avium complex, PML)	Discontinue acalabrutinib
Grade 3 confirmed bacterial infections	
 
Hold acalabrutinib
 
If infection does not respond to appropriate antimicrobial therapy within 48 to 72 hours, discontinue acalabrutinib
 

Grade 4 confirmed bacterial infections	Discontinue acalabrutinib
Other	
Any non-COVID-19-related Grade 4 AE	Discontinue acalabrutinib
Any other Grade 3 or Grade 4 toxicity that persists despite optimal medical management	Discontinue acalabrutinib

AE = adverse event; ALT = alanine aminotransferase; ANC = absolute neutrophil count; ALP = alkaline phosphatase; AST = aspartate aminotransferase; G-CSF = granulocyte colony-stimulating factor; PML = progressive multifocal leukoencephalopathy.

Clinical judgment should be used to determine appropriate management of the participant during any AE.

Acalabrutinib may be held for a maximum of 3 consecutive days (6 consecutive doses) from expected dose due to toxicity. If a dose is missed due to an AE or for any other reason, missed

doses should be completed so the participant receives a maximum of 28 doses of acalabrutinib, even if this is beyond the 14-day dosing period.

## **6.6.1 Acalabrutinib Dose Modifications in Special Populations**

### **6.6.1.1 Renal Impairment**

After administration of a single 100 mg radiolabeled acalabrutinib dose in healthy participants, 84% of the dose was recovered in the feces and 12% of the dose was recovered in the urine (2% acalabrutinib). No clinically relevant PK difference was observed in participants with mild or moderate renal impairment (eGFR  $\geq 30$  mL/min/1.73 m^2, as estimated by MDRD equation). Acalabrutinib PK and clinical safety has not been evaluated in participants with severe renal impairment (eGFR  $< 29$  mL/min/1.73 m^2, MDRD) or renal impairment requiring dialysis.

The effect of dialysis on acalabrutinib plasma concentrations has not been studied. Acalabrutinib is rapidly absorbed, metabolized, and distributed. The plasma-protein binding is 97.5% and is noncovalent (potentially dialyzable). However, acalabrutinib covalently binds to the target, BTK, and will not be dialyzable. As such, it is unlikely that a clinically meaningful lowering of total BTK occupancy in target cell populations will be impacted. If participants with COVID-19 enrolled in this study require acute hemodialysis, it is recommended to dose acalabrutinib 100 mg and pause hemodialysis for 2 to 4 hours after acalabrutinib administration to allow for absorption and distribution to target cell populations.

